7.2. Detailed Study Procedures

VISIT 1

The subject must present to Visit 1 wearing their habitual contact lenses on the day of the visit.

Visit 1: Screening		
Step	Procedure	Details
1.1	Statement of Informed Consent	Each subject must read, understand, and sign the Statement of Informed Consent before being enrolled into the study. The Principal Investigator or his/her designee conducting the informed consent discussion must also sign the consent form. Note: The subject must be provided a signed copy of this document.
1.2	Demographics	Record the subject's date of birth, gender, race and ethnicity.
1.3	Medical History and Concomitant Medications	Questions regarding the subjects' medical history and concomitant medications.
1.4	Habitual Lenses	Questions regarding the subject's habitual lens type and parameters.
1.5	Eligibility after Screening	All responses to Screening Inclusion Criteria questions must be answered "yes" and all responses to Exclusion Criteria must be

		answered “no” for the subject to be considered eligible.	
--	--	--	--

Visit 1: Baseline			
Step	Procedure	Details	
1.6	Baseline Questionnaire	The subject will respond to the CLUE™ Baseline Handling Questionnaire (Appendix A)	
1.7	Entrance Visual Acuity	Record the distance Snellen visual acuity (OD, OS, and OU) to the nearest letter with their habitual contact lens correction in place. Subjects must read the smallest line until at least 50% of the letters are read incorrectly.	
1.8	Subjective Sphero-cylindrical Refraction	Complete subjective sphero-cylindrical refraction and record the resultant distance visual acuity (OD, OS and OU) to the nearest letter.	
1.9	Subjective Best Sphere Refraction	
Perform subjective best sphere refraction with a phoropter (adopt the maximum plus to maximum visual acuity (MPMVA) approach and use the duo-chrome test for binocular balancing) and record the best corrected distance visual acuity (OD, OS, OU) to the nearest letter.
 
Note: The endpoint criterion for the duo-chrome test is the lens power at which the red and green sides of the chart appear to be equally distinct. However, if the subject's response changes from “red” to “green” with only a 0.25D change in power and no report that the two sides appear to be equally sharp, the refraction endpoint should be the lens power that leave the red chart sharper.
	

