1.10	Slit Lamp Findings	
FDA Slit Lamp Classification Scale will be used to grade the findings and determine eligibility.
 
If any of these slit lamp findings are Grade 3 or higher, the subject may not continue at this time, but may return up to one additional time to determine eligibility. If discontinued a final examination must be completed.
 
If the clearance of the fluorescein needs to be expedited, preservative-free rewetting drops or saline may be instilled.
	

1.11	Eligibility after Baseline	All responses to Inclusion Criteria questions must be answered “yes” and all responses to Exclusion Criteria questions must be answered “no” for the subject to be considered eligible.	
------	----------------------------	---	--

Visit 1: Treatment 1 Lens Fitting			
Step	Procedure	Details	
1.12	Lens Selection	Assign the study lens based on the randomization scheme. Select the contact lens power based on subjective best sphere refraction.	
1.13	Lens Insertion	The Investigator or the subject inserts the study lenses. Record the time of lens insertion. Check for lens damage under the slit lamp before proceeding with lens settling. Replace damaged lenses if applicable. Note: If a damaged lens needs to be replaced, the subject will have to return no sooner than the following day, since subjects are not allowed to wear more than one lens per eye per day. When a subject returns for another lens, new baseline information must be recorded (starting with step 1.7), and then proceed per protocol through the remaining Visit 1 steps.	
1.14	Lens Settling	Allow the study lenses to settle for a minimum of 15 minutes.	
1.15	Subjective Best Sphere Over Refraction	Perform subjective best sphere refraction over the study lenses with a phoropter (adopt the maximum plus to maximum visual acuity (MPMVA) approach and use the duo-chrome test for binocular balancing) and record the best corrected distance visual acuity to the nearest letter (OD, OS, OU). Note: The endpoint criterion for the duo-chrome test is the lens power at which the red and green sides of the chart appear to be equally distinct. However, if the subject's response changes from “red” to “green” with only a 0.25D change in power and no report that the two sides appear to be equally sharp, the refraction endpoint should be the lens power that leave the red chart sharper.	

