1.16	Lens Power Modification (if applicable)	
Adjust the lens power if the subject's best sphere over-refraction is not plano.
 
One power modification is allowed. If the subject's best sphere over-refraction is not plano, the subject will have to return no sooner than the following day, since subjects are not allowed to wear more than one lens per eye per day. When a subject returns for another lens, new baseline information must be recorded (starting with step 1.7), and then proceed per protocol through the remaining Visit 1 steps.
	
1.17	Subject Reported Ocular Symptoms	Subjects will respond to a verbal open-ended symptoms questionnaire.	
1.18	Subjective Lens Fit Assessment	
Evaluate overall lens fit acceptance (acceptable or unacceptable) based on centration, movement and other fitting characteristics.
 
An unacceptable fit is deemed by one of the following criteria:
 
 • limbal exposure at primary gaze or with extreme eye movement; • edge lift; • excessive movement in primary and up gaze; or • insufficient movement in all three of the following conditions: primary gaze, up gaze, and push up test. 
Note: if lens fit is unacceptable subject will be discontinued from the study.
	
1.19	Distance ETDRS LogMAR Visual Acuity	
Perform monocular distance ETDRS LogMAR visual acuity test at a 4-meter distance over the test eye only under the following condition:
 
 • bright illumination (e.g., >400 lux), high luminance, with high contrast charts (HLHC); 
The Precision Vision 4-meter high contrast ETDRS charts (Chart 1 and Chart 2) will be used.
 
One measurement will be recorded per eye.
	

1.20	Exit Snellen VA	Record subjects' distance visual acuity, OD, OS and OU to the nearest letter. [REDACTED]	
1.21	Continuance	For the subject to continue in the study, they must meet all three of the following criteria: 
 • Visual acuity is 20/30 or better OD and OS • The lens fit is acceptable OD and OS • Investigator approval. If the Investigator does not approve the dispensing of the first study lens, then the study is terminated for that subject. 	

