14.5. Primary Analysis

Contact lens monocular distance best-corrected visual acuity on logMAR scale will be analyzed using a linear mixed effects model to test for non-inferiority of K-Lens relative to Placebo. Lens group will be included as fixed effects in the model; and investigator site as random effect. The covariance matrix between the left eye visual acuity and right eye visual acuity will be selected based on the finite-sample Corrected Akaike's Information Criterion.²⁴ Covariance structures considered include Compound Symmetry (CS) and Unstructured (UN). The covariance structure that returns the lowest AICC will be selected as the structure that best fit the data. Heterogeneous covariance structures across study lens groups will be considered

when appropriate. The log-likelihood ratio test will be used to test for the homogeneity between the residual covariance structures. The Kenward and Roger method will be used to calculate the denominator degree of freedom.²⁵

The null and alternative hypotheses for non-inferiority of K-Lens relative to Placebo are as follows:

$$\begin{aligned} H_0: \Delta \geq 0.1 \\ H_A: \Delta < 0.1, \end{aligned}$$

where Δ is the mean difference in visual acuity between K-Lens and Placebo (K-Lens minus Placebo). The non-inferiority test will be based on the least-square mean difference (K-Lens minus Placebo) and corresponding 95% confidence interval calculated using the final selected model. The upper bound of the 95% confidence interval will be compared to the non-inferiority margin of 0.1 LogMAR. If the upper bound is less than 0.1, K-Lens will be considered non-inferior to Placebo with respect to visual Acuity.

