6.2. Baseline Disease Characteristics

The following baseline clinical characteristics will be summarized at subject level by treatment arm:

- CLUE™ Baseline Handling Questionnaire;

- Entrance distance Snellen Visual Acuity with their habitual contact lens correction in place.

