8.1. Primary Efficacy Endpoint

Primary analysis will be run on monocular contact lens-corrected distance visual acuity using a logMAR visual acuity scale measured at follow-up visit (Visit 2) for each eye.

This will be analyzed using a linear mixed effects model to test for non-inferiority of K-Lens relative to Placebo. LogMar score is assumed to be normally distributed and this will be verified visually with a QQ-plot of residuals, using the stored SAS output obtained from fitting the linear mixed model, and tested with a normality test. Lens group will be included as fixed effects in the model and investigator site as random effect.

Let y_{ijkl} be the visual acuity measured on the i th eye, $i = [\text{Left, Right}]$, of the j th subject, $j = 1, 2, \dots, n_l$, assigned to the k th treatment, $k = 1, 2$, in the l th investigational site, $l = 1, 2, \dots, 5$. The proposed statistical model for the primary analysis is

$$y_{ijkl} = \mu + Treatment_k + Site_l + \varepsilon_{i(jkl)}, \text{ where}$$

- μ : overall mean;
- $Treatment_k$: effect of the k^{th} treatment, a fixed effect;
- $Site_l$: effect of the l^{th} investigational site, a random effect;
- $\varepsilon_{i(jkl)}$: random error associated with the i^{th} eye of the j^{th} subject assigned to the k^{th} treatment in the l^{th} investigational site.

Here we assume $site_l$ and $\varepsilon_{ij(kl)}$ are independent and

- $site_l \sim N(0, \sigma_{site}^2)$;
- $\begin{bmatrix} \varepsilon_{Left(jkl)} \\ \varepsilon_{Right(jkl)} \end{bmatrix} \sim N \left(\begin{bmatrix} 0 \\ 0 \end{bmatrix}, \begin{bmatrix} \sigma_{11}^2 & \sigma_{12} \\ \sigma_{21} & \sigma_{22}^2 \end{bmatrix} \right)$.

While the site effect and the error term will have a diagonal covariance matrix, there will be a correlation between the visual acuity of eyes belonging to the same subject. The model will take this into account using an unstructured covariance matrix (UN) between left and right eye. Should the estimation algorithm not converge, then a Compound Symmetry matrix (CS) will be used. In this case, the assumption is that observations coming from different eyes will have the same variance.

$$\begin{bmatrix} \varepsilon_{Left(jkl)} \\ \varepsilon_{Right(jkl)} \end{bmatrix} \sim N \left(\begin{bmatrix} 0 \\ 0 \end{bmatrix}, \begin{bmatrix} \sigma^2 & \sigma_{12} \\ \sigma_{21} & \sigma^2 \end{bmatrix} \right)$$

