The log-likelihood ratio test will be used to test for the homogeneity between the residual covariance structures across treatment groups. The Kenward and Roger method will be used to calculate the denominator degree of freedom.²⁵

The null and alternative hypotheses for non-inferiority of K-Lens relative to Placebo are as follows:

$$H_0: \Delta \geq 0.1$$
$$H_A: \Delta < 0.1$$

where Δ is the mean difference in visual acuity between K-Lens and Placebo (K-Lens minus Placebo). The non-inferiority test will be based on the least-square mean difference (K-Lens minus Placebo) and corresponding 95% confidence interval calculated using the final selected model. The upper bound of the 95% confidence interval will be compared to the non-inferiority margin of 0.1 LogMAR. If the upper bound is less than 0.1, K-Lens will be considered non-inferior to Placebo with respect to visual acuity.

The following code will be used to run the mixed model.

```
proc glimmix data = dataset plots=ResidualPanel;
class treatment siteid subjid eye;
model logmar = treatment/ DDFM=KenwardRoger S;
random intercept /subject = siteid;
random eye / type=matrix_cov subject=subjid(siteid) group = treatment
residual;
lsmeans treatment / diff=control('Placebo') cl;
covtest 'Common Variance' Homogeneity;
ods output ParameterEstimates=parms Covtests=mixcovtest
CovParms=mixcovp diffss=diffs lsmeans=lsmeans;run;
```

Where:

- “Treatment” is the treatment group variable (K-Lens/Placebo);
- “Siteid” is the investigator site identifier;
- “Eye” is the variable to identify which eye the observation belongs to (left/right);
- “Subjid” is the subject identifier;
- “Matrix_cov” is the covariance structure (UN/CS) between the left eye visual acuity and right eye visual acuity.

If the hypothesis of homogeneity is accepted (chi-square test p-value > 0.05) the syntax “group = treatment” and the ‘covtest’ statement will be omitted from the final model.

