12.3. SAS Code for Sensitivity Analysis

The following SAS code will be used to generate the sensitivity analysis for the difference in visual acuity logMAR score (K-Lens versus Placebo), using a MI process for imputation of missing data.

Multiple imputation phase

```
proc mi data= yyyyyyy nimpute=20 seed=51343672 out=outmi ;
  class SITEID TREATMENT;
  var SITEID TREATMENT LOGMARV1_OD LOGMARV1_OS LOGMARV2_OD LOGMARV2_OS;
  fcs discrim(SITEID TREATMENT /classeffects=include) reg (LOGMARV1_OD LOGMARV1_OS LOGMARV2_OD
LOGMARV2_OS /details);
run;
```

In case the analysis of the missing data will show a monotone pattern, the same procedure will be executed with the MONOTONE statement.

```
proc mi data= yyyyyyy nimpute=20 seed=51343672 out=outmi ;
  class SITEID TREATMENT;
  var SITEID TREATMENT LOGMARV1_OD LOGMARV1_OS LOGMARV2_OD LOGMARV2_OS;
  monotone discrim (SITEID TREATMENT /classeffects=include) reg (LOGMARV1_OD LOGMARV1_OS
LOGMARV2_OD LOGMARV2_OS /details);
run;
```

where LOGMARV1_OD is the logmar score at the last visit, excluding unscheduled, prior to visit 2 for the right eye;
LOGMARV1_OS is the logmar score at the last visit, excluding unscheduled, prior to visit 2 for the left eye;
LOGMARV2_OD is the logmar score at visit 2 for the right eye;
LOGMARV2_OS is the logmar score at visit 2 for the left eye;
SITEID is site identifier within each study;
TREATMENT is the treatment variable (K-Lens/Placebo);

Analysis by imputation at each visit

```
proc glimmix data = outmi;
by _imputation_;
class treatment siteid subjid eye;
model logmar = treatment/ DDFM=KenwardRoger S;
random intercept /subject = siteid;
random eye / type=UN subject=subjid(siteid) group = treatment residual;
lsmeans treatment / diff=control('Placebo') cl;
covtest 'Common Variance' Homogeneity;
ods output ParameterEstimates=mixparms Covtests=mixcovtest CovParms=mixcovp diffss=diffs
lsmeans=lsmeans;
run;
```

If the hypothesis of homogeneity is accepted (chi-square test p-value > 0.05) the syntax “group = treatment” and the ‘covtest’ statement will be omitted from the final model.

The model will take into account using UN covariance matrix for each imputation dataset. In case the algorithm will not converge with the UN for a particular dataset, then the CS matrix will be used for such imputation dataset. This will be reviewed on a case by case basis.

Results combined for the inference at each timepoint and visit

```
proc mianalyze data=diffs;
modeleffects estimate;
stderr stderr;

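### The primary model is valid and adequately powered, but it leaves out acuity recorded before randomisation; a subject-mean covariate could narrow the deciding confidence interval at almost no cost.

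*SAP*

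**What the plan says.** SAP 8.1 fits a linear mixed model to the Visit 2 logMAR scores of both eyes: "Lens group will be included as fixed effects in the model and investigator site as random effect". Protocol 14.5 has the same terms: "Lens group will be included as fixed effects in the model; and investigator site as random effect". The two eyes are linked by an unstructured residual covariance, with compound symmetry as the fallback. In the GLIMMIX code the fixed part is "model logmar = treatment/ DDFM=KenwardRoger S", and the by-imputation code in SAP Appendix 12.3 repeats that statement. The imputation model there lists "var SITEID TREATMENT LOGMARV1_OD LOGMARV1_OS LOGMARV2_OD LOGMARV2_OS", so the only earlier acuity it uses is Visit 1 logMAR.

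Other acuity data exist. At Visit 1 step 1.9 (Protocol 7.2) the site performs a best-sphere refraction and must "record the best corrected distance visual acuity (OD, OS, OU) to the nearest letter". Only at step 1.12 does the instruction "Assign the study lens based on the randomization scheme" follow. SAP 6.2 uses baseline acuity descriptively ("The following baseline clinical characteristics will be summarized at subject level by treatment arm"), and the value listed there is entrance Snellen acuity with habitual lenses, taken at step 1.7.

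After a damaged lens or a power change (steps 1.13 and 1.16) the baseline is repeated: "When a subject returns for another lens, new baseline information must be recorded (starting with step 1.7"). SAP section 4 then takes the last of the repeated baselines for summary and analysis.

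**The concern.** Non-inferiority is declared when the upper 95% confidence bound for K-Lens minus Placebo lies below 0.1 logMAR, so the width of that interval enters the decision directly. A measure of the same construct, taken in each eye before randomisation, is already in the database. If it predicts Visit 2 acuity, leaving it out makes the interval wider than it need be.

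The choice of covariate also needs care, because two convenient candidates are unsuitable:

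- **Visit 1 logMAR** (step 1.19) is on the right scale and already in the imputation code, but it is measured with the assigned lens on the eye. Adjusting for it could remove part of the lens effect under test.
- **The last baseline under SAP section 4** can fall after randomisation and study-lens wear for subjects who return for a replacement lens or a power change.

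**Working it through.** **Inputs.** Margin 0.1 logMAR (Protocol 2.3, SAP 8.1). Two-sided 5% level, so one-sided 0.025 for the upper bound. Difference 0.04, SD 0.10, n = 117, between-eye correlation 1, 2:1 allocation, 80/40 completers (SAP 4.1). The correlation ρ between the subject-mean baseline and the subject-mean outcome is not in the documents; 0 to 0.5 is assumed.

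**The plan's own figure.** With a noncentral-t calculation, the smallest total in multiples of three that gives 85% power at difference 0.04 and SD 0.10 is 117 (power 85.9%), as SAP Table 2 states. Rows 0/0.05 (15) and 0.04/0.05 (33) also reproduce. The row printed with SD 0.01 and n = 45 reproduces only with SD 0.10, which does not affect this point.

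**Unadjusted at 80/40.**
- SE = 0.10 × √(1/80 + 1/40) = 0.01936
- Noncentrality = (0.10 − 0.04)/0.01936 = 3.098 on 118 df; power 86.7%
- Half-width = 1.9803 × 0.01936 = 0.0383

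**With one subject-level covariate.** SD becomes 0.10 × √(1 − ρ²), with 117 df.

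| Assumed ρ | SD | Half-width | Power |
|---|---|---|---|
| 0 | 0.1000 | 0.0384 | 86.7% |
| 0.1 | 0.0995 | 0.0382 | 87.0% |
| 0.3 | 0.0954 | 0.0366 | 89.6% |
| 0.5 | 0.0866 | 0.0332 | 94.4% |

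The interval is 0.5%, 4.6% and 13.4% narrower at ρ = 0.1, 0.3 and 0.5. At ρ = 0 the half-width rises by less than 0.00001 (0.03835 either way; the table differs only by rounding). Simulation of subject means (8,000 runs per setting) agreed, with one-sided type I error at the margin of 0.023 to 0.026 with and without the covariate.

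**Less pessimistic cases.** If the between-eye outcome correlation is 0.8, SD = 0.10 × √(1.8/2) = 0.0949. Unadjusted power is then 90.0% and half-width 0.0364, against 0.0362, 0.0347 and 0.0315 at ρ = 0.1, 0.3 and 0.5. At difference 0 and SD 0.10, unadjusted power is already 99.9%.

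**Form of the covariate.** Both eyes receive the same lens, so only between-subject variation affects the treatment contrast. Two-eye simulation used 1,500 runs per setting, compound symmetry, no site effect, between-eye correlation 0.98 for outcome and 0.8 (assumed) for baseline, and each baseline eye equally correlated with both outcome eyes. Monte Carlo SE of power is at most about 0.9 points.

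| Eye-pair correlation (subject-mean) | Half-width: unadjusted / eye-specific / subject mean | Power |
|---|---|---|
| 0.5 (0.53) | 0.0381 / 0.0373 / 0.0325 | 85.7 / 86.9 / 94.7% |
| 0.3 (0.32) | 0.0380 / 0.0377 / 0.0362 | 87.2 / 87.8 / 90.5% |

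At 0.1 neither form gains materially (0.0380 / 0.0380 / 0.0379). In the first row the eye-specific slope averages only 0.05, because nearly equal outcomes in the two eyes pull it towards zero. Adding each eye's deviation from the mean left the half-width unchanged.

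**The case against.** The strongest reply is that nothing is broken. Protocol and SAP agree, the only stratification factor (site) is in the model, the estimate is unbiased and the stated power is met. All of that stands.

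It also stands that the gain depends on an unknown correlation. Entry requires 20/30 or better in each eye (Protocol 3.2), step 1.21 requires it again with the study lens, and phoropter acuity is not study-lens ETDRS acuity; each may keep the correlation low. Outside the worst case there is little power to gain: at SD 0.10, unadjusted power is 94.8% for a difference of 0.03 and 98.4% for 0.02.

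The calculations carry no site effect. If 10% or 20% of the variance lay between sites (assumed), the planned model would already reach about 90.0% or 93.0% power, and any correlation acting through site would already be captured. The gain could then be smaller than tabulated.

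Finally, the poor showing of the eye-specific covariate depends on the equal-correlation assumption. With 0.53 for the same eye and 0.47 for the fellow eye, its large-sample half-width is 0.0336 against 0.0324 for the subject mean. With outcome correlation 0.8 and 0.55/0.45, both give 0.0303. The penalty can therefore be small, but the subject mean was not worse in any case checked.

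These points limit the size of the gain. They do not count against taking it at so little cost.

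**Conclusion.** The point holds as a recommended improvement, not a correction. In the plan's worst case the covariate would cut the half-width from 0.0383 to between 0.0382 and 0.0332 logMAR and raise power from 86.7% to between 87.0% and 94.4%, for assumed correlations of 0.1 to 0.5. In more favourable scenarios the benefit is a narrower interval, with little change in the chance of declaring non-inferiority. The case for acting is the asymmetry between a possible gain and a negligible loss, in a design whose binding scenario needs 117 of the 120 planned completers. Confidence in the size is medium, because the correlation, the between-eye baseline correlation and the share of variance between sites are all assumptions.

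**What to change.** Before unmasking, amend the SAP as follows:

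1. In 8.1, add one fixed covariate: the subject mean of the right- and left-eye best-sphere acuities from step 1.9, converted to logMAR by a written rule for the chart used. The readable text of step 1.9 names no chart, so the sponsor must supply the rule.
2. Define it as the last step 1.9 value before both randomisation and first study-lens insertion, as an explicit exception to the repeated-baseline rule in section 4.
3. Add it to the MODEL statements in 8.1 and Appendix 12.3 and to the PROC MI VAR list, so that the imputation and analysis models match. In the wide imputation data set it is one column per subject.
4. Do not use the eye-specific value alone, and do not adjust for Visit 1 logMAR. Each eye's deviation from the mean may be a second term, but whether it is included must be settled in advance; in simulation it added nothing.
5. Keep the unadjusted model as a sensitivity analysis.

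SAP section 1 gives the SAP precedence over Protocol section 14, so an SAP change is enough.

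The cost is one degree of freedom (two with the deviation term), a few lines of text and code, and the conversion rule. No new data are needed.

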2.3. Hypotheses

Primary Hypotheses

The K-Lens will be non-inferior to the Placebo lens with respect to monocular distance contact lens-corrected visual acuity. A non-inferiority margin of 0.1 logMAR (one line) units will be used.

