3.1. Overall Study Design and Plan

This is a randomized, double-masked, bilateral, controlled, two-arm parallel group, multi-site, 1-week dispensing study. Approximately 132 subjects will be screened and randomly assigned to either K-Lens or Placebo using 2:1 ratio (i.e. 2/3 of subjects on the K-Lens arm and 1/3 on the Placebo arm). The goal is for a sample size of 120 (80 subjects in K-lens and 40 subjects in Placebo) after subjects who withdraw or are lost-to-follow-up.

The study begins with an Initial Visit (Visit 1). If a subject is found to meet all eligibility criteria, they will be randomized and fit with either the K-Lens or Placebo lens in both eyes based on the randomization scheme provided to the investigators; otherwise, the subject will be deemed ineligible for this study.

Successfully dispensed subjects at the initial visit will be scheduled for a follow-up visit (Visit 2). The follow-up visit will occur approximately 6 to 9 days after the Initial Visit. Unscheduled follow-up visits may occur during the study. Subjects will be advised to wear the study lenses at least 8 hours a day for a minimum of 6 days.

Both study lenses will be worn as a daily disposable modality. J&J Vision Care (JJVC) will provide the investigational sites with sufficient quantities of study lenses and supplies to complete the study.

The Investigator is responsible for ensuring that all subjects entering the study conform to subject selection criteria. The number of subjects targeted for randomization and completion are as follows:

Table 1: Target number of subjects by arm and site

	K-Lens	Placebo	Total
Randomization	88	44	132
Completion	80	40	120
Number of sites	6	6	6
Subjects/site (Min-Max)	12-16	5-9	20-24

The schedule of events is reported in section 12.1.

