- Reason for discontinuation
- Unscheduled lens replacement
- Reasons for unscheduled lens replacement including lens damage.

4. General Statistical Considerations

Continuous data will be summarized descriptively by n, mean, standard deviation (SD), median, minimum (Min) and maximum (Max). Minimum and maximum will be presented to the same number of decimal places as the raw data, mean and median will be presented to 1 more decimal place than the raw data, and standard deviation will be presented to 2 more decimal places than the raw data.

Categorical data will be summarized descriptively by frequency: n (%). The denominator for all percentages will be the number of subjects (or eyes as applicable) available, once pooled, within that treatment group for the analysis set of interest, unless otherwise indicated. Percentages will be presented to 1 decimal place and will not be displayed for zero frequencies. A row denoted “Missing” will be included in count tabulations where necessary to account for missing values.

All data summaries and statistical analyses will be performed using the SAS software version 9.3 or higher (SAS Institute, Cary, NC).

All planned analysis will be conducted with an overall type I error rate of 5%. Unless otherwise specified, all statistical tests will be 2-sided.

P-values will be rounded to 3 decimal places. P-values that round to 0.000 will be presented as '<0.001' and p-values that round to 1.000 will be presented as '>0.999'.

Study day of an event that occurred after or on the first Fitting date will be calculated as Event Date – First Fitting Date + 1.

Study day of an event that occurred before the first dose date will be calculated as Event Date – First Fitting Date.

Baseline is last assessment obtained prior to the insertion of the test or control lenses, unless otherwise specified. Some subjects may have up to four baseline evaluations if a damaged lens needs to be replaced and/or due to failure to fulfil inclusion criteria and/or due to fulfilment of exclusion criteria. In this case, the last baseline evaluation will be considered in the descriptive summary and analysis. For subjects enrolled but not randomized the last non-missing assessment will be taken as baseline.

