4.1. Sample Size

Assuming a perfect correlation between left eye visual acuity and the right eye visual acuity (worst case scenario), the total sample size (n) required to achieve 85% power with two-

sided type I error of 0.05 was calculated for different scenarios of mean difference (Δ = K-Lens – Placebo) and common standard deviation (σ) in the two arms. The results are summarized in the Table below:

Table 2: Sample size for different scenarios of mean Δ and σ

Δ	σ	n
0	0.05	15
0	0.01	45
0.04	0.05	33
0.04	0.1	117

The sample size calculation was conducted using the PROC POWER Procedure (SAS/STAT 14.1, SAS Institute, 2015) for two-sample means with allocation weight of 2:1.

The sample size of 120 subjects is considered sufficiently large to test for non-inferiority with a minimum statistical power of 85% and two-sided type I error of 0.05.

The plan is to enroll 132 eligible subjects with a target completion of 120 subjects (80 subjects in K-Lens and 40 subjects in Placebo).

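### A low-power variance test picks the standard error of the non-inferiority interval and, separately, the mean model has no eye term; under assumed but moderate conditions coverage falls one to two points below 95%

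*SAP*

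**What the plan says.** The decision rule in SAP 8.1 is a single comparison: "The upper bound of the 95% confidence interval will be compared to the non-inferiority margin of 0.1 LogMAR". Protocol 2.3 sets the margin: "A non-inferiority margin of 0.1 logMAR (one line) units will be used". The interval comes from whichever model is finally selected.

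The selection works as follows. The GLIMMIX code fits a left/right residual covariance separately by arm (`group = treatment`) and tests whether the arms share it. The rule then reads "If the hypothesis of homogeneity is accepted (chi-square test p-value > 0.05) the syntax" and goes on to remove `group = treatment`. Unstructured (UN) covariance is the default; compound symmetry (CS) is used only if UN does not converge.

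For the mean, SAP 8.1 states "Lens group will be included as fixed effects in the model and investigator site as random effect". The MODEL statement contains treatment alone, and eye enters only through the residual covariance. The written model equation shows one covariance matrix with no arm index, which does not match the code.

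SAP 12.3 repeats the homogeneity rule alongside code run by imputation, and it allows UN or CS to vary between imputed datasets. Protocol 14.5 says only that heterogeneous structures are considered when appropriate; SAP 1 makes the SAP govern over Protocol Section 14.

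**The concern.** There are two separate weaknesses, and curing one leaves the other.

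First, the data-driven choice of standard error. Under 2:1 allocation a pooled variance is dominated by the larger arm. If the smaller Placebo arm is the more variable one, the pooled standard error is too small and the non-inferiority test is anti-conservative. A pre-test protects against this only if it has power, and at 80 against 40 it has little for moderate differences.

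Second, the missing eye term. With UN covariance and a common mean for both eyes, the arm mean is a generalised least squares (GLS) average with estimated left/right weights. When each arm has its own matrix, each has its own weights, so a right-left mean difference need not cancel between arms. The model standard error does not carry the noise in those weights.

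At stake is the nominal level of the one interval that decides the primary question.

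**Working it through.** **Inputs from the documents.** 80 K-Lens and 40 Placebo completers, margin 0.1, two-sided 5%, common SD up to 0.1, between-eye correlation 1 as worst case (SAP 3.1, 4, 4.1, 8.1). **Assumed, because the documents give no value:** arm-specific SDs, between-eye correlation 0.5 to 0.9, OD-OS mean difference δ of 0 to 0.04, site SD 0.02.

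**1. The plan's own figure.** N = (1.960 + 1.036)² × σ² × 4.5 / (0.1 − Δ)². With Δ = 0.04 and σ = 0.1 this is 8.98 × 0.01 × 4.5 / 0.0036 = 112.2, or 114 in multiples of 3. The noncentral t gives 117, as printed, and also reproduces 15 and 33. The row printed with SD 0.01 and n = 45 reproduces only at SD 0.1 and looks like a misprint. Power at 80/40 for Δ = 0.04, σ = 0.1 is 86.7%. All of this assumes equal SDs.

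**2. Error in a pooled standard error.** Take K-Lens SD 1 and Placebo SD 1.25 (relative units).
- True variance: 1/80 + 1.5625/40 = 0.05156.
- Pooled: [(79 × 1 + 39 × 1.5625)/118] × (1/80 + 1/40) = 1.1859 × 0.0375 = 0.04447.
- Standard-error ratio: √(0.04447/0.05156) = 0.929. Always pooling would therefore cover about 93%; simulation gives 93.0%.
- With the SDs swapped: true 0.04453, pooled 0.05162, ratio 1.077, so the interval is too wide.

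**3. The pre-test rule, no eye difference** (SD 0.1 in K-Lens unless stated, correlation 0.7, 3-df likelihood ratio test, 60,000 runs, Kenward-Roger-type inflation):

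| Placebo/K-Lens SD | Coverage | One-sided error |
|---|---|---|
| 1.00 | 95.1% | 2.5% |
| 1.15 | 94.1% | 2.9% |
| 1.25 | 94.0% | 2.9% |
| 1.35 | 94.5% | 2.7% |
| 1.50 | 94.9% | 2.6% |
| 2.00 | 95.0% | 2.6% |
| K-Lens 1.25 times larger | 95.5% | 2.2% |

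At ratio 1.25 the test rejects in 44% of trials. A second simulation (correlation 0.8, 20,000 runs, no Kenward-Roger or site effect) gave 46% rejection, 93.8% coverage and 3.2% error. A full REML fit with random site (4,000 runs) gave 94.4% and 2.8%.

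**4. Eye weights and bias.** In an arm with UN covariance the GLS weight on the right eye is w = (σ²_OS − σ₁₂)/(σ²_OD + σ²_OS − 2σ₁₂). The bias in K-Lens minus Placebo is (w_K − w_P) × δ, with δ = OD minus OS. Equal eye SDs give w = 0.5 whatever the scale, so a pure difference in spread between arms gives no bias. If Placebo OS SD is 0.125 against OD 0.1 (correlation 0.7), w_P = (0.015625 − 0.00875)/(0.025625 − 0.0175) = 0.846. Then (0.5 − 0.846) × δ is −0.003, −0.007 and −0.014 for δ = 0.01, 0.02 and 0.04. Whole-plan coverage in those cases is 94.2%, 93.0% and 89.1%, with error 3.5%, 4.8% and 8.9%. The sign reverses if the pattern does.

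**5. Standard-error shortfall without bias.** Let s be the mean of the two eyes and d = OD − OS. The arm mean is s̄ − b·d̄, with b the estimated slope of s on d. With equal eye SDs, noise in b multiplies the arm's variance by about 1 + δ²/Var(d), where Var(d) = 2σ²(1 − ρ). The model omits this factor, apart from any small-sample adjustment. For δ = 0.02 and ρ = 0.7:
- K-Lens, SD 0.1: 1 + 0.0004/0.006 = 1.067.
- Placebo, SD 0.125: 1 + 0.0004/0.009375 = 1.043.
- Arm variances, σ²(1 + ρ)/2 divided by n: 0.000106 and 0.000332. The weighted factor is 1.048, so the standard error is about 2.4% too small.
- The branch then covers about 94.4%; the REML check gave 94.6%.

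In the pooled branch b is common, so b·δ cancels. Under CS the weights are equal and b is zero.

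**6. Both routes together, SD ratio 1.25, δ = 0.02.** Whole-plan coverage is 93.6% (SDs 0.10/0.125, correlation 0.7) and 93.1% (0.08/0.10, correlation 0.8, no Kenward-Roger). The REML check gave 94.1%, with a Monte Carlo error of √(0.94 × 0.06/4000) = 0.4 points.

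**7. After the change.** Arm-specific variance with equal eye weights gave 94.9 to 95.1% coverage and 2.4 to 2.5% error in all seven scenarios tried. REML with separate matrices and an eye effect gave 95.5% and about 2.2%.

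**The case against.** The rule is fully pre-specified, with threshold and code, and the loss from the pre-test alone is about one point. The harmful direction needs the marketed lens to be the more variable one, and the documents give no reason to expect that; a variable new manufacturing line would push the other way, where the plan is slightly conservative. All of that stands and limits the weight of the point.

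The eye difference is also an assumption. Protocol 7.2 says "The Precision Vision 4-meter high contrast ETDRS charts (Chart 1 and Chart 2) will be used", with one measurement per eye. A reader might infer that each eye gets its own chart, or that a fixed testing order builds in a difference. The text assigns neither chart nor order, and the detailed procedure in Appendix D is redacted, so balanced or alternated testing cannot be ruled out.

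A reader might also infer that the missing eye term does harm whenever the arms differ in spread. It does not: with no OD-OS mean difference the arm-specific branch covers 94.8 to 95.1% at every SD ratio tried.

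Nor does the arm-specific branch on its own represent the plan. Forcing it at equal SDs of 0.08 with δ = 0.02 and correlation 0.8 gives about 92%, but there the plan pools in about 95% of trials, and two simulations put its coverage at 93.9% and 94.6%.

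Finally, SAP 12.3 serves a sensitivity analysis. It does not clearly say that the homogeneity choice is made per imputed dataset, and it leaves non-convergence to case-by-case review. Mixing of models across imputations is possible there, not certain.

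**Conclusion.** The point holds as a modest one with two parts.

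- **Pre-test.** If the Placebo SD is about 1.15 to 1.35 times the K-Lens SD, coverage is about 94% and one-sided error about 2.9 to 3.2% (slightly less at the upper end of that range). The effect nearly vanishes at ratios of 1.5 or more, where the test usually rejects.
- **Eye term.** This matters only in the arm-specific UN branch and only with a non-zero OD-OS mean difference. At an assumed 0.02 and SD ratio 1.25, whole-plan coverage is about 93 to 93.6%, with the REML check a little higher. Bias arises only if the left/right variance pattern also differs by arm; those figures rest on a closed-form simulation alone. For K-Lens more variable with an eye difference of 0.02, simulations disagree (93.4%, 94.4%, 94.8%), so I put no figure on that case.

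It would be wrong to infer that the trial's conclusion is in danger. With SD 0.1 and correlation 0.7 the half-width is about 1.98 × √(0.0085 × 0.0375) = 0.035, and about 0.04 with Placebo SD 0.125, against a margin of 0.1. At a true difference of zero, power is 98% or more in every post-change scenario. The exposure is to a true difference close to the margin. Kenward-Roger was approximated, not run in SAS.

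**What to change.** Before unmasking, edit SAP 8.1 and 12.3:

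- Always keep `group = treatment` on the residual RANDOM statement, and report the homogeneity test descriptively only.
- Change the mean model to `model logmar = treatment eye / DDFM=KenwardRoger S`.
- Use one covariance structure for all 20 imputed datasets, and state the fallback if any of them fails to converge.
- Give the written covariance matrix an arm index so that it matches the code.

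The cost is one extra fixed-effect parameter and an interval about 1% wider or less if the variances are in fact equal. Power at a true difference of 0.04 (correlation 0.7) is 91% with equal SDs of 0.1 and 80% if the Placebo SD is 0.125; that drop comes from the larger variance, not from the change.
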